9.6 Data Management and Storage Process

9.6.1 Data Management

Data management and data quality check will be performed to remove errors and inconsistencies in order to assure the appropriateness of the study data set to assess the study objectives. Data entry screens will be developed and tested prior to initiating data collection to reduce data entry errors. If required, IMS will provide AbbVie with data for analysis.

Each principle investigator or his/her designees will be instructed to answer patients' queries which may arise in relation to the questionnaires and check the patients' input to make sure all questions are answered.

9.6.2 Storage Process

Following data quality checks, each dataset will be converted to SAS and merged for analysis. All information included in the CRF and the patients' questionnaires will be checked in order to detect possible queries to solve and will be extracted to a specifically designed database, where it will be validated by IMS personnel to ensure its quality. Finally, data analysis will be conducted and final results reported.

The databases will be stored in IMS data servers. Data servers are submitted to daily backups in order to increase the security on all data managed in the collection process.

All paper based questionnaires will be stored in a secured, locked area for a period of seven (7) years, after which all data will be shared using an agency specialized in disposal of confidential documents.

9.7 Data Analysis

9.7.1 Statistical and Analytic plans

A statistical analysis plan (SAP) will be developed describing the specific analysis that will be performed including, and in addition to, the analysis described here. All analysis will be performed in accordance with the approved analysis plan. The following provides an overview of some of the analysis.

The scoring of the PRO questionnaires will be done in accordance to the developers' recommendations.

A separate statistical analysis plan will be developed describing the specific analysis that will be performed including and in addition to the analysis described here.

9.7.2 Analyzable population

All subjects who received at least one dose of adalimumab during the study will be included. The main analysis will be conducted on the pooled population, where appropriate, with each individual country analyzed separately as supportive data.

9.7.3**Planned Methods of Statistical Analysis**

All statistical tests will be two-tailed with a significance level of 0.05. Descriptive statistics will be provided. Descriptive analysis will be conducted on all key parameters and presented as mean, standard deviation, minimum, maximum, and median when continuous and as “n” and percent when categorical. Change from adalimumab initiation to 24 weeks will be calculated and evaluated for significant improvements using paired t-tests / ANOVA for parametric and Wilcoxon signed-rank for non-parametric data. Analysis will be also be conducted by severity level (moderate vs severe), disease duration quartile (to compare to prior work) and up to two (2) other subgroups. Cochran-Armitage test of trends or other similar methods may be used to compare categories of subjects.

9.7.4**Primary Endpoint Analysis**

The primary endpoint variable will be the change in HAQ DI score at 24 weeks after the initiation of adalimumab (observed population).

The objective of the primary endpoint analysis will be to demonstrate that treatment with adalimumab improves functioning as measured by the HAQ DI in subjects with RA following treatment initiation. This change will be summarized as the mean and 95% confidence interval and will be tested with a paired t-test.

The primary analysis will be summarized as the mean and 95% confidence interval and will be tested with a paired t-test without adjusting for baseline disease severity. For sensitivity analysis, the mean change in HAQ DI at Week 24 will be analyzed using ANOVA adjusting for baseline disease severity.

9.7.5**Secondary Endpoint Analysis**

The main secondary endpoint variable will be the change in HAQ DI at 12 weeks after the initiation of adalimumab.

The objective of endpoint analysis will be to demonstrate that treatment with adalimumab improves functioning as measured by HAQ DI in subjects with RA compared to baseline.

The main secondary analysis will be summarized as the mean and 95% confidence interval and will be tested with a paired t-test without adjusting for baseline disease severity. For sensitivity analysis, the mean change in HAQ DI at Week 12 will be analyzed using ANOVA adjusting for baseline disease severity.

Other secondary analysis include:

- Change in other patient reported outcomes (SF-36 domain scales, EQ-5D Index, WPAI total lost productivity) at weeks 12 and 24 after the initiation of adalimumab, in those patients continuing on adalimumab (observed population). These changes will be summarized as the means and 95% confidence intervals and will be tested with paired t-tests.
- Number and percent of patients achieving a clinically meaningful improvement on the HAQ DI, as defined by a -0.22 point improvement or greater, at weeks 12 and 24 after the initiation of adalimumab (observed population).

9.7.6 Additional Secondary Endpoint Analysis

Additional efficacy analysis includes:

- Change in HAQ DI score at 24 weeks after the initiation of adalimumab, in those patients continuing on adalimumab, compared with those patients not continuing on adalimumab. The mean changes in these two groups will be compared using an independent t-test.
- Healthcare resource utilization will be described using number and percentage within each category (number of consultations, number of procedures received, number of surgeries, number of hospitalizations and length of stay, number of concomitant medications)
- Associations between disease severity and PROs
- Associations between change in disease severity and change in PROs

Exploratory endpoint

Change in patient satisfaction questions at weeks 12 and 24 after the initiation of adalimumab (observed population). These changes will be summarized as number and percentage of each response and compared with Kruskal-Wallis test. Satisfaction will also be dichotomized and analyzed over time with Cochrane-Armitage test for trends.

9.7.7 Safety Analysis

Adverse events occurring while participants are on adalimumab will be coded using Common Terminology Criteria for Adverse Events (CTCAE) classification individually listed by indication groups. The incidences and percentages of individuals experiencing AEs and SAEs within each indication will be summarized by System Organ Class (SOC) with further summaries by severity and relatedness (causality) categories. Adverse events

leading to discontinuation and concomitant medications will also be listed and summarized.

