9.0 Research Methods

9.1 Study Design

This study is designed as a prospective, observational study to assess the effect of adalimumab on health-related QoL and work productivity in patients with RA in Korea in clinical practice.

Note: This study is non-interventional and the subjects/investigators will follow the current clinical practice in each site and also the routine clinical follow up as determined by the treating physician.

RA patients will be recruited from within the clinical settings of each rheumatologist participating in the study. Approximately 89 patients diagnosed with RA that meet the inclusion and exclusion criteria will be enrolled at approximately 9 sites in Korea.

To assess health and disability outcomes, the HAQ DI will be assessed at baseline, Week 12 and Week 24 after treatment initiation with adalimumab. In addition, other PROs of work activity and well-being, including the WPAI, EQ-5D, and SF-36, will also be assessed.

The patients identified by the recruiting investigators (specialty dependent on country/region; e.g. rheumatologist, internists, general practitioners, etc.) based on the study selection criteria will complete a set of patient questionnaires on QoL, functioning, work productivity, treatment satisfaction, impression of change and HCRU. Data will be captured at baseline (D0), Week 12 and Week 24.

The HCRU will also be collected. This includes surgical procedures, hospitalizations, bed days in hospital, physician consultations etc. Costs will be assigned based on the HCRU using standardized costs for each participating countries.

Subjects may discontinue adalimumab treatment at any time during study participation. Subjects that end study participation early will have a Termination Visit. All subjects will have a follow-up phone call approximately 70 days after the last administration of adalimumab to obtain information on any new or ongoing AEs.

This protocol requires all SAEs and AESIs as outlined in protocol section 11.0 to be actively solicited. The safety profile of adalimumab which has over 3.5 million patient years of post-marketing exposure is stable and well established; non-serious events will not be actively solicited as these events are not likely to contribute to the further understanding of the safety profile of the product. Any non-serious AEs will be collected as spontaneous reports if AbbVie is notified.

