9.1.1 Schedule of Events

Table 1 Study Activities (Day 1/Baseline Through 6 months)

	Study Activity	Baseline ^a	Week 12 (V2) ± 7 days	Week 24 (V3) ± 7 days	Early Termination / Drop out
Clinician Packet	Inclusion/exclusion form	X			
	Clinical history/patient demographics	X			
	Comorbidities	X			
	DAS28 (ESR) or DAS28 (CRP)	X	X	X	X
Patient Packet	EuroQoL 5-Dimension (EQ-5D)	X	X	X	X
	Short Form 36-Item Health Survey (SF-36)	X	X	X	X
	Health Assessment Questionnaire (HAQ)	X	X	X	X
	Work Productivity and Activity Impairment Questionnaire (WPAI)	X	X	X	X
	Healthcare Resource Utilization (HCRU)	X	X	X	X
	Patient Global Impression of Change (PGIC)		X	X	X
	Patient Treatment Satisfaction Questions	X	X	X	X
	Adverse events (including malignancy)	X	X	X	X

a. The Baseline visit date will serve as the reference for all subsequent visits. A ± 7 day window is permitted around scheduled study visits.

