9.2.5 Adverse Events

Adverse events, whether in response to a query, observed by site personnel, or reported spontaneously by the subject will be recorded. Adverse events definition and serious adverse event categories are described in detail in Section 11.0.

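### Protocol 9.7.7 plans all-AE incidences although non-serious AEs are, by 9.1 and 9.4, only spontaneous reports; the percentages are likely too low and the ascertainment wording is inconsistent

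*Protocol*

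**What the plan says.** Protocol 9.7.7 covers adverse events that occur on adalimumab. It states that "The incidences and percentages of individuals experiencing AEs and SAEs within each indication will be summarized by System Organ Class (SOC". The same section then splits these figures by severity and by causal assessment. It does not limit the AE part to serious, special-interest or spontaneously reported events, and it attaches no caveat to the percentages. The analysable population in Protocol 9.7.2 is everyone who received at least one dose.

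How events reach the database is described in several places, and not in the same way:

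- **Protocol 9.1** on solicited events: "This protocol requires all SAEs and AESIs as outlined in protocol section 11.0 to be actively solicited". On the rest: "non-serious events will not be actively solicited as these events are not likely to contribute to the further understanding of the safety profile", and "Any non-serious AEs will be collected as spontaneous reports if AbbVie is notified".
- **Protocol 9.4** names only spontaneous adverse events among the data collected.
- **Protocol 9.2.5**: "Adverse events, whether in response to a query, observed by site personnel, or reported spontaneously by the subject will be recorded".
- **Table 1 (Protocol 9.1.1)** has a row beginning "Adverse events (including malignancy", marked at baseline, Week 12, Week 24 and early termination.
- **Protocol 9.1** also gives every subject a phone call about 70 days after the last dose, "to obtain information on any new or ongoing AEs".
- **Protocol 17.0** has an AE that causes treatment discontinuation reported to the sponsor within 24 hours, whether serious or not.

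The SAP does not settle the matter. Its analysis sections (5.1 to 5.6) and its list of tables (section 6) contain no safety analysis.

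**The concern.** The percentage of patients with an event estimates its incidence only if patients who have the event can be expected to appear as cases. Under the rule in 9.1, a patient with a non-serious event that nobody reports counts as a patient without one. The error runs in one direction, downward.

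The same summary would carry SAE percentages that rest on active solicitation. A reader would see two figures under one label and nothing to show that they were gathered differently.

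There is a second, lesser issue. With about 9 sites, a site that follows 9.1 closely and a site that takes 9.2.5 and Table 1 as a prompt to ask about all AEs could record different proportions at the same true risk.

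The breakdown by severity has a related weakness. Protocol 11.1.2 defines severity ratings for AEs collected as an endpoint or data point and for all SAEs. It is not stated whether a spontaneous non-serious report falls within that, so some events may lack the rating that 9.7.7 would tabulate.

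**Working it through.** **Setting the passages side by side**

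| Event type | Route into the data | Does a percentage of treated patients estimate incidence? |
|---|---|---|
| SAEs | Actively solicited (9.1) | Yes, on this ground |
| AESIs | Actively solicited (9.1), but Section 11 as available here labels no events as AESIs | Yes, once the category is listed |
| Non-serious AEs leading to discontinuation | 24-hour reporting (17.0) | Largely |
| Other non-serious AEs | Spontaneous report (9.1, 9.4) | No; likely too low |

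Section 9.7.7 pools all four rows into its AE figure.

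Three passages point towards wider ascertainment: 9.2.5, the AE row in Table 1 and the 70-day call. None is limited to serious events. The call is weaker evidence for this purpose, because it falls after the last dose while 9.7.7 covers events on treatment. The baseline and follow-up forms reproduced in Appendix C show no AE item, and the Early Termination Form in Appendix K lists an AE only as a reason for stopping. The forms shown therefore do not standardise capture.

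**Size: illustration only**

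The documents state no AE rate, so there is no figure of theirs to reproduce. The only inputs they supply are the planned size of about 89 (Protocol 9.5: 40/0.5/(1 − 0.1) = 88.9, rounded to 89) and about 9 sites (9.1). The other inputs are assumptions:

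- p = true proportion of patients with at least one non-serious AE, taken as 30% to 70%
- c = probability that such a patient appears in the data without being asked, taken as 25% to 75%
- f = share of patients at sites that ask about all AEs, with capture there set to 1

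Expected observed proportion = p × (f + (1 − f) × c).

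With p = 50% and N = 89, full capture would give 0.50 × 89 = 44.5 patients. Otherwise:

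| c | No site asks (f = 0) | Half the patients at asking sites (f = 0.5) |
|---|---|---|
| 25% | 12.5% (11.1 patients) | 31.25% (27.8) |
| 50% | 25.0% (22.2) | 37.5% (33.4) |
| 75% | 37.5% (33.4) | 43.75% (38.9) |

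Across the assumed ranges with f = 0, the observed proportion runs from 0.30 × 0.25 = 7.5% to 0.70 × 0.75 = 52.5%. For between-site differences, take p = 50% and c = 50%: sites that ask would show 50% and sites that do not would show 25%, at the same true risk. If every site asks (f = 1), the observed proportion equals p and the shortfall disappears.

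The all-AE percentage falls short by at most the same number of patients, because a missed patient who also had an SAE is still counted.

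**The case against.** The strongest reply is that the passages can be read together. Section 9.2.5 governs what is recorded and orders no query about non-serious events. SAEs and AESIs must be solicited in any case, so the AE row in Table 1 can be that solicitation. On this reading sites ask about serious and special-interest events and write down whatever else they hear, which agrees with 9.4. That is a fair reading. It removes any claim that the protocol instructs sites to query for non-serious AEs. It does not help 9.7.7, because it confirms that the non-serious part of the AE percentage rests on unprompted reports.

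A reader might infer that the percentages will certainly be understated and will certainly differ by site. The documents do not support that. No passage describes differing site practice, and the two effects depend on different conditions: if all sites ask, the understatement largely disappears, and if none ask, sites do not differ on this account. Both occur together only if practice is mixed, which is possible but not stated.

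It is also true that safety is not among the stated objectives, that there is one arm and no comparator, and that 9.1 declares the collection policy openly. No passage plans to present the non-serious rate as favourable evidence. These points limit the consequence. They do not make the figure an incidence.

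**Conclusion.** The point holds in a limited form. If the plan is followed as written, Protocol 9.7.7 yields an all-AE incidence whose non-serious component comes from spontaneous reports. That component, and so the all-AE percentage, is likely to be too low. The direction follows from 9.1 and 9.4, provided at least some sites apply them. The size cannot be derived from the documents, and the illustrative figures show direction only.

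SAE percentages are not affected on this ground, and non-serious AEs that lead to discontinuation are less exposed. The inconsistency between 9.1 and 9.4 on one side and 9.2.5, Table 1 and the 70-day call on the other is real as a matter of wording. Capture could therefore differ between sites; it cannot be said that it will. No efficacy endpoint is touched. This should be corrected, but it is a matter of how safety results are reported and labelled.

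**What to change.** 1. In Protocol 9.7.7, and in a safety table added to the SAP, give incidence percentages only for systematically collected events: SAEs, AESIs once Section 11 lists them, and AEs leading to discontinuation.
2. Present other non-serious AEs as listings or patient counts, headed as spontaneously reported and not an incidence.
3. Reconcile 9.1, 9.2.5, 9.4, Table 1 and the 70-day call to one stated ascertainment rule. Which rule is for the sponsor to decide; this review does not choose. If that rule turns out to be systematic questioning about all AEs, and sites did so, step 2 is unnecessary.
4. Data collection was planned to end on 28 February 2018 and the Amendment 01 approvals are dated March to April 2018, so rewording may come too late to alter collection. In that case the report should state how non-serious AEs were actually ascertained.

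The cost is wording, table headings, one SAP table and a list of AESIs. No new patients or data are needed. The downside is that no headline all-AE incidence would be reported.

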9.7.8 Additional Analysis

Additional analysis will explore the potential modifying effects of baseline measures on the changes in primary and secondary efficacy outcomes. These measures will include age, gender, baseline severity, and other diagnoses/co-morbidities. The analysis will specifically test for differential changes across the subgroups defined by the potential modifiers using general linear models.

9.7.9 Missing Data

Efficacy measures are not assessed after a participant discontinues adalimumab. The exception to this will be the analysis of proportion of patients at 24 weeks who remain on adalimumab. Item level data on the PROs will be imputed according to the developers' recommendations. There will be no other imputation for missing data.

9.7.10 Interim Analysis

There is no interim analysis planned for this study.

9.8 Quality Control

9.8.1 Ethics and Quality

Prior to any study-related data being collected, informed consent form will be reviewed, signed and dated by the patient and the person who administered the informed consent. A copy of the signed informed consent will be given to the patient and the original will be placed in the patient's medical record.

9.8.2 Quality Assurance

Prior to the initiation of the study, physician and site personnel will be trained on the study. Training will include a detailed discussion of the protocol, performance of study procedures, and completion of the CRFs and paper questionnaires.

All sites will be monitored during the course of study participation. One hundred percent (100%) source document review for safety will be performed.

All clinical data will be documented via the CRF. Study coordinators at each site will check the paper CRFs completed by the physicians and questionnaires completed by patients (e.g., all questions were answered). Data entry will be conducted by IMS. After entry of the data, computer logic checks will be run to check for inconsistent data. Any necessary corrections will be made to the database and documented via addenda, queries, and source data clarification forms.

Steps to be taken to ensure the accuracy and reliability of data include the selection of qualified investigators and appropriate study centers, review of protocol procedures with the investigator and associated personnel before the study and periodic monitoring visits by the sponsor. Written instructions will be provided for administration and collection of study questionnaires.

Guidelines for CRF completion will be provided and reviewed with study personnel before the start of the study. The sponsor will review CRFs and patient questionnaires for accuracy and completeness after transmission to the sponsor; any discrepancies will be resolved with the investigator or designee, as appropriate. After upload of the data into the clinical study database they will be verified for accuracy and consistency with the data sources.

9.9**Limitations of the Research Methods**

The study is to be performed as a non-interventional study. Unlike clinical studies, obtainable data are limited and there is a possibility of missing data.

9.10**Other Aspects****9.10.1****Note to File**

The Principal Investigator or designee will be responsible for documenting study relevant information and occurrences that affects the course of the study. The information and occurrences are not protocol deviations but will be documented in a note to file and will be communicated to the sponsor.

9.10.2 Training Log

All designated study personnel must be trained on the study protocol and procedures. Training and retraining are documented on the Training Log.

9.10.3 Visitor Log

All Sponsor or other related individuals who visit the study site must sign the Visitor Log.

9.10.4 Responsibilities of the Principal Investigator

The Principal Investigator is responsible for oversight of enrolment, the patient consent process, study related procedures, compliance with the protocol, all institutional, state and local guidelines.

It is the responsibility of the Principal Investigator to select, supervise, and delegate responsibility for study conduct to staff members. The Principal Investigator is responsible for determining the appropriate staff qualifications required for specific study-related tasks to be delegated. Study-related tasks delegated to staff members will be documented on the Site Signature and Delegation Log.

9.10.5 End of Trial

End of Trial is defined as last subject's last visit (LSLV).

10.0 Protection of Human Subjects

This study must be conducted in compliance with the recommendations of the Declaration of Helsinki, 2008 (World Medical Association). In addition, this study will adhere to all general and local legal and regulatory requirements applicable to non-interventional studies.

Informed consent will be obtained from each subject before the subject can participate in the study. The contents and process of obtaining informed consent will be in accordance with all applicable regulatory requirements.

As required by applicable local regulations, the sponsor's Regulatory Affairs group will ensure all legal regulatory aspects are covered, and obtain approval of the appropriate regulatory bodies, prior to study initiation in regions where an approval is required.

This study is non-interventional and falls outside the scope of the EU Directive 2001/20/EC, the EU Directive 2005/28/EC and International Conference on Harmonization (ICH) Good Clinical Practice (GCP) guidelines.

This study complies with the EU Directive 95/46/EC of the European Parliament and of the Council of 24 October 1995 on the protection of individuals with regard to the processing of personal data and on the free movement of such data.

